4.5.2 Premedication

Routine premedication should not be administered for the prevention of infusion-related reactions prior to the first dose of study drug(s). However, subjects should be carefully monitored for infusion reactions during administration of study drug(s). If an acute infusion reaction is noted, subjects should be managed according to [Section 4.5.6](#).

Subjects should be individually evaluated to assess the need for tumor lysis prophylaxis prior to the first dose of brentuximab vedotin. Subjects should receive prophylaxis as appropriate per the institutional standards.

4.5.3 Dose Modifications for Brentuximab Vedotin

Table 4.5.3-1 describes the recommended dose modifications for brentuximab vedotin treatment associated toxicity. Doses reduced for brentuximab vedotin-related toxicity should not be re-escalated without discussion with the sponsor. Dose escalation of brentuximab vedotin beyond 1.8 mg/kg is not permitted.

Dose reductions below 1.2mg/kg are not allowed, and toxicities should be managed with dose delays.

If brentuximab vedotin treatment is delayed for any reason, nivolumab must also be delayed until the subject has appropriately recovered and is able to resume the combination treatment on the first day of the subsequent cycle. Nivolumab should only be given alone in case a decision has been made to permanently discontinue brentuximab vedotin.

Table 4.5.3-1: Dose Modifications for Brentuximab Vedotin				
Toxicity	Grade 1	Grade 2	Grade 3	Grade 4
Peripheral Neuropathy	Continue at same dose level	Reduce dose to 1.2 mg/kg and resume treatment ^a	Withhold (delay) until toxicity resolves to ≤ Grade 2 or baseline, then resume treatment at 1.2 mg/kg or discontinue if reduction has already occurred.	Discontinue treatment

Table 4.5.3-1: Dose Modifications for Brentuximab Vedotin				
Toxicity	Grade 1	Grade 2	Grade 3	Grade 4
Non-hematologic (except peripheral neuropathy)	Continue at same dose level	Continue at same dose level	Withhold (delay) dose until toxicity is ≤ Grade 2 or has returned to baseline, then resume treatment at the same dose level ^b	Withhold dose until toxicity is ≤ Grade 2 or has returned to baseline, then reduce dose to 1.2 mg/kg and resume treatment, or discontinue at the discretion of the investigator ^{a,b, c}
Hematologic ^d	Continue at same dose level	Continue at same dose level	Withhold (delay) until toxicity resolves to ≤ Grade 2 or baseline, then resume treatment at the same dose level ^e . Growth factor support (G-CSF or GM-CSF) should be considered for subsequent cycles. If Grade 4 neutropenia recurs despite growth factor support, consider discontinuation or dose reduction to 1.2 mg/kg.	

^a Dose reductions below 1.2 mg/kg are not allowed, and toxicities should be managed with dose delays.

^b Subjects who develop Grade 3 or 4 electrolyte laboratory abnormalities may continue study treatment without dose delay.

^c Treatment should be discontinued for subjects who experience Grade 4 infusion-related reactions.

^d Support with blood product transfusions allowed per institutional standard of care.

^e Subjects who develop Grade 3 or 4 lymphopenia may continue study treatment without dose delay.

Subjects who discontinue nivolumab due to a related AE may continue treatment with brentuximab vedotin monotherapy until disease progression or unacceptable toxicity. Similarly, subjects who discontinue brentuximab vedotin due to related AE may choose to continue on nivolumab monotherapy. In the Cohort A, if toxicity is observed during the DLT evaluation period that requires discontinuation of study treatment, both compounds must be discontinued.

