4.5.4 Dose Modifications for Nivolumab

4.5.4.1 Nivolumab Dose Delays

Dose delay criteria apply for all drug-related AEs. Nivolumab must be delayed until treatment can resume (see [Section 4.5.4.2](#))

Nivolumab administration should be delayed for the following:

- Any Grade ≥ 2 non-skin, drug-related AE, with the following exceptions:
 - Grade 2 drug-related fatigue or laboratory abnormalities do not require a treatment delay
- Any Grade 3 skin, drug-related AE

- Any Grade 3 drug-related laboratory abnormality, with the following exceptions for lymphopenia, leukopenia, AST, ALT, total bilirubin, or asymptomatic amylase or lipase:
 - Grade 3 lymphopenia or leukopenia does not require dose delay.
 - If a subject has a baseline AST, ALT, or total bilirubin that is within normal limits, delay dosing for drug-related Grade ≥ 2 toxicity.
 - If a subject has baseline AST, ALT, or total bilirubin within the Grade 1 toxicity range, delay dosing for drug-related Grade ≥ 3 toxicity.
- Any AE, laboratory abnormality, or intercurrent illness which, in the judgment of the investigator, warrants delaying the dose of study medication.

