4.5.4.2 Criteria to Resume Nivolumab Dosing

Subjects may resume treatment with nivolumab when the drug-related AE(s) resolve to Grade ≤ 1 or baseline value, with the following exceptions:

- Subjects may resume treatment in the presence of Grade 2 fatigue
- Subjects who have not experienced a Grade 3 drug-related skin AE may resume treatment in the presence of Grade 2 skin toxicity
- Subjects with baseline AST/ALT or total bilirubin in the Grade 1 toxicity range who require dose delays for reasons other than a 2-grade shift in AST/ALT or total bilirubin may resume treatment in the presence of Grade 2 AST/ALT OR total bilirubin
- Subjects with combined Grade 2 AST/ALT AND total bilirubin values meeting discontinuation parameters ([Section 4.5.5](#)) should have treatment permanently discontinued
- Drug-related pulmonary toxicity, diarrhea, or colitis must have resolved to baseline before treatment is resumed
- Drug-related endocrinopathies adequately controlled with only physiologic hormone replacement may resume treatment.

If nivolumab treatment is delayed for any reason, brentuximab vedotin must also be delayed until the subject has appropriately recovered and is able to resume the combination treatment on the first day of the subsequent cycle. Brentuximab vedotin should only be given alone in case a decision has been made to permanently discontinue nivolumab.

If treatment is delayed > 6 weeks, the subject must be permanently discontinued from study therapy, except as specified in [Section 4.5.5](#).

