4.5.5 Nivolumab Treatment Discontinuation

Nivolumab treatment should be permanently discontinued for the following:

- Any Grade 2 drug-related uveitis or eye pain or blurred vision that does not respond to topical therapy and does not improve to Grade 1 severity within the re-treatment period OR requires systemic treatment
- Any Grade 3 non-skin, drug-related AE lasting > 7 days, with the following exceptions for drug-related laboratory abnormalities, drug-related uveitis, pneumonitis, bronchospasm, hypersensitivity reactions, and infusion reactions:
 - Grade 3 drug-related uveitis, pneumonitis, bronchospasm, hypersensitivity reaction, or infusion reaction of any duration requires discontinuation
 - Grade 3 drug-related endocrinopathies adequately controlled with only physiologic hormone replacement do not require discontinuation
 - Grade 3 drug-related laboratory abnormalities do not require treatment discontinuation except:
 - ◆ Grade 3 drug-related thrombocytopenia > 7 days or associated with clinically significant bleeding requires discontinuation
 - ◆ Any drug-related liver function test (LFT) abnormality that meets the following criteria require discontinuation:
 - AST or ALT > 8 x ULN
 - Total bilirubin > 5 x ULN
 - Concurrent AST or ALT > 3 x ULN and total bilirubin > 2 x ULN
- Any Grade 4 drug-related AE or laboratory abnormality, except for the following events which do not require discontinuation:
 - Grade 4 neutropenia ≤ 7 days
 - Grade 4 lymphopenia or leukopenia
 - Isolated Grade 4 electrolyte imbalances/abnormalities that are not associated with clinical sequelae and are corrected with supplementation/appropriate management within 72 hours of their onset
 - Grade 4 amylase or lipase abnormalities that are not associated with symptoms or clinical manifestations, or radiographic signs of pancreatitis. It is recommended to consult with the BMS Medical Monitor for Grade 4 amylase or lipase abnormalities
 - Grade 4 drug-related endocrinopathy AEs such as adrenal insufficiency, ACTH (Adrenocorticotropic Hormone) deficiency, hyper- or hypothyroidosis, or glucose intolerance, which resolve or are adequately controlled with physiologic hormone replacement (steroids, thyroid hormones) or glucose controlling agents, respectively, may not require discontinuation after discussion with and approval from the BMS Medical Monitor

- Any dosing delay lasting > 6 weeks from the previous dose with the following exceptions:

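### Footnote b of Table 4.5.3-1 waives any dose delay for Grade 3 or 4 electrolyte abnormalities, against the nivolumab rules for drug-related Grade 3 events (delay) and for drug-related Grade 4 events outside the 72-hour exception (permanent stop)

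*Protocol*

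**What the plan says.** Protocol 4.5.3 opens by giving the scope of its table: "Table 4.5.3-1 describes the recommended dose modifications for brentuximab vedotin treatment associated toxicity". Footnote b is attached to the Grade 3 and Grade 4 cells of the non-hematologic row, which otherwise call for withholding the dose. It reads: "Subjects who develop Grade 3 or 4 electrolyte laboratory abnormalities may continue study treatment without dose delay".

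Nivolumab has its own rules:

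- Protocol 4.5.4.1 lists among the grounds for delay: "Any Grade 3 drug-related laboratory abnormality, with the following exceptions for lymphopenia, leukopenia, AST, ALT, total bilirubin, or asymptomatic amylase or lipase". Electrolytes are not among the exceptions. A separate item covers adverse events: "Any Grade ≥ 2 non-skin, drug-related AE, with the following exceptions". Those exceptions are limited to Grade 2 fatigue and Grade 2 laboratory abnormalities.
- Protocol 4.5.5 says of Grade 3: "Grade 3 drug-related laboratory abnormalities do not require treatment discontinuation except", and then names only thrombocytopenia and liver-function criteria. Of Grade 4 it lists as a ground for permanent discontinuation: "Any Grade 4 drug-related AE or laboratory abnormality, except for the following events which do not require discontinuation". One of those excepted events is: "Isolated Grade 4 electrolyte imbalances/abnormalities that are not associated with clinical sequelae and are corrected with supplementation/appropriate management within 72 hours of their onset".

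The two drugs are tied together in Protocol 4.5.4.2: "If nivolumab treatment is delayed for any reason, brentuximab vedotin must also be delayed". SAP 7.4.2.1 repeats the tie in both directions.

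**The concern.** The footnote speaks of study treatment, not of brentuximab vedotin, and its permission is unconditional. A site that looks up a low potassium or sodium result in Table 4.5.3-1 would dose on schedule. A site that looks up the same drug-related result under the nivolumab sections would hold both drugs or, for some Grade 4 events, stop nivolumab for good. No clause was found that says which section prevails.

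This reaches the analysis by two routes. Protocol 4.5.1 defines a DLT as a drug-related toxicity that requires a dose reduction, or a delay of more than 7 days, of either drug in Cycle 2, or that delays Cycle 3 Day 1 by more than 7 days. SAP 7.6.1 adds discontinuation for Cohort A. What counts as required depends on the section applied. Second, adverse events leading to dose delay and to discontinuation are primary safety endpoints (Protocol 8.3.1, SAP 4.1). The situation can recur: Table 5.1-2 schedules calcium, magnesium, potassium, chloride and sodium before dosing on Cycle 1 Day 8 and on Day 1 of every later cycle.

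**Working it through.** There is no figure to reproduce, so the check sets the passages side by side by grade and relatedness.

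1. **Drug-related, Grade 3.** Footnote b: no delay. Section 4.5.4.1: delay nivolumab, since electrolytes are not exempt. Section 4.5.4.2: nivolumab resumes at Grade 1 or lower or at baseline, and brentuximab vedotin waits with it. Section 4.5.5: no discontinuation. This is a direct conflict over delay.

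2. **Drug-related, Grade 4, not isolated, or with sequelae, or not corrected within 72 hours.** Footnote b: continue. Section 4.5.5: permanently discontinue nivolumab. They conflict if the footnote's term covers nivolumab. If it covers brentuximab vedotin alone, Sections 4.5.3 and 4.5.5 allow brentuximab vedotin monotherapy afterwards and the conflict falls away, except in the Cohort A DLT period, when both drugs must stop.

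3. **Drug-related, Grade 4, isolated, no sequelae, corrected within 72 hours.** Section 4.5.5 does not require a stop. A conflict over delay can remain only through the general adverse-event item in 4.5.4.1, while the event is unresolved.

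4. **Not drug-related.** The mandatory nivolumab laboratory criteria do not apply; only investigator judgment does. No conflict.

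**Does a brentuximab-only reading remove case 1?** Only by cancelling the permission. If nivolumab must be delayed, 4.5.4.2 also delays brentuximab vedotin, so for a drug-related Grade 3 result on combination treatment the footnote can never be used.

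**Comparison with footnote e.** The same table gives the same permission for Grade 3 or 4 lymphopenia. That one is matched elsewhere: 4.5.4.1 exempts Grade 3 lymphopenia from delay, and 4.5.5 exempts Grade 4 lymphopenia from discontinuation. Electrolytes have no exemption from delay and only a conditional one from discontinuation. This points to an omission, though the documents do not say so.

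**Thresholds for the analysis.** SAP 7.4.2.1 counts a dose as delayed only beyond 3 days from schedule, and the DLT definition needs more than 7 days. A hold that clears within 3 days enters neither SAP count.

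**The case against.** The strongest reply is that the scope is stated. The table concerns brentuximab vedotin, footnote b qualifies that table's own hold, and it is permissive, whereas the nivolumab and linked-delay rules are mandatory. On that reading there is one answer: the table imposes no hold of its own, 4.5.4.1 may impose one, and the link carries it across. The footnote still has work to do for unrelated abnormalities and for brentuximab vedotin monotherapy. This reading is possible. But it departs from the footnote's wording, and the text just below the table uses the same term where it says both compounds must be discontinued. A site has to assemble the answer from three sections, and nothing tells it to do so.

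Four stronger readings are tempting and are not supported:

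- A reader might infer that one result can lead to no delay, delay or permanent discontinuation. Grade 3 electrolyte abnormalities do not by themselves reach discontinuation under 4.5.5, and Grade 4 events do so only outside the stated exception.
- A reader might see a second contradiction in asymptomatic Grade 3 amylase or lipase, which is exempt from nivolumab delay but held under the brentuximab vedotin table. Section 4.5.3 makes nivolumab wait whenever brentuximab vedotin is delayed, so there is a single outcome.
- A reader might size the problem by applying an assumed rate of Grade 3 or 4 electrolyte events to the 136 treated subjects planned. The documents give no rate, and only the drug-related subset is at issue.
- A reader might conclude that the expansion decision could be overturned. The rule in 4.5.1 allows at most 1 DLT in 6 subjects, so in principle one reclassified subject matters. But the toxicity must require a delay of more than 7 days (or, under the SAP, discontinuation), the study team may revise DLT classifications, and SAP 7.1 speaks in the past tense of the single dose explored in Cohort A. That decision had probably been taken.

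**Conclusion.** The inconsistency stands in a limited form. For drug-related Grade 3 electrolyte abnormalities, footnote b conflicts with 4.5.4.1, and the linked-delay rule extends the conflict to brentuximab vedotin. For drug-related Grade 4 abnormalities outside the 72-hour exception, it conflicts with 4.5.5, provided that the footnote's term includes nivolumab.

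Its size cannot be expressed as a number of subjects. It rests on how many drug-related events occur, how long any hold lasts, and which section each site follows, none of which the documents give. In Cohort A what remains is probably DLT classification and reporting. In Cohort B it is comparability across sites of exposure and of the delay and discontinuation counts. Those summaries are descriptive, so no test or error rate is affected. This is worth correcting because it touches primary safety endpoints and the remedy is cheap.

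**What to change.** Reconcile footnote b with Protocol 4.5.4.1, 4.5.4.2 and 4.5.5, so that Grade 3 and Grade 4 electrolyte abnormalities each have one rule per drug, with relatedness stated. Say whether the footnote covers brentuximab vedotin only or both drugs, and how it operates when the linked delay applies. The clinical team chooses the rule; this review takes no view on it.

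Then apply the reconciled rule in the DLT classification (SAP 7.6.1), the dose-delay tabulation (SAP 7.4.2.1) and the discontinuation tabulation (SAP 7.4.2.3). For events handled before the clarification, list any electrolyte-related delay or discontinuation with grade, relatedness and duration, so that a reader can see which reading was followed.

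The cost is a protocol clarification by administrative letter or in the next amendment, plus a short SAP note. It adds no procedures, visits or samples.

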4.5.4 Dose Modifications for Nivolumab

4.5.4.1 Nivolumab Dose Delays

Dose delay criteria apply for all drug-related AEs. Nivolumab must be delayed until treatment can resume (see [Section 4.5.4.2](#))

Nivolumab administration should be delayed for the following:

- Any Grade ≥ 2 non-skin, drug-related AE, with the following exceptions:
 - Grade 2 drug-related fatigue or laboratory abnormalities do not require a treatment delay
- Any Grade 3 skin, drug-related AE

- Any Grade 3 drug-related laboratory abnormality, with the following exceptions for lymphopenia, leukopenia, AST, ALT, total bilirubin, or asymptomatic amylase or lipase:
 - Grade 3 lymphopenia or leukopenia does not require dose delay.
 - If a subject has a baseline AST, ALT, or total bilirubin that is within normal limits, delay dosing for drug-related Grade ≥ 2 toxicity.
 - If a subject has baseline AST, ALT, or total bilirubin within the Grade 1 toxicity range, delay dosing for drug-related Grade ≥ 3 toxicity.
- Any AE, laboratory abnormality, or intercurrent illness which, in the judgment of the investigator, warrants delaying the dose of study medication.

4.5.4.2 Criteria to Resume Nivolumab Dosing

Subjects may resume treatment with nivolumab when the drug-related AE(s) resolve to Grade ≤ 1 or baseline value, with the following exceptions:

- Subjects may resume treatment in the presence of Grade 2 fatigue
- Subjects who have not experienced a Grade 3 drug-related skin AE may resume treatment in the presence of Grade 2 skin toxicity
- Subjects with baseline AST/ALT or total bilirubin in the Grade 1 toxicity range who require dose delays for reasons other than a 2-grade shift in AST/ALT or total bilirubin may resume treatment in the presence of Grade 2 AST/ALT OR total bilirubin
- Subjects with combined Grade 2 AST/ALT AND total bilirubin values meeting discontinuation parameters ([Section 4.5.5](#)) should have treatment permanently discontinued
- Drug-related pulmonary toxicity, diarrhea, or colitis must have resolved to baseline before treatment is resumed
- Drug-related endocrinopathies adequately controlled with only physiologic hormone replacement may resume treatment.

If nivolumab treatment is delayed for any reason, brentuximab vedotin must also be delayed until the subject has appropriately recovered and is able to resume the combination treatment on the first day of the subsequent cycle. Brentuximab vedotin should only be given alone in case a decision has been made to permanently discontinue nivolumab.

If treatment is delayed > 6 weeks, the subject must be permanently discontinued from study therapy, except as specified in [Section 4.5.5](#).

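### For certain Grade 2 drug-related events the brentuximab vedotin table and the nivolumab hold with its linked delay cannot both be followed, and the protocol does not say which prevails

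*Protocol*

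**What the plan says.** Three provisions meet on the same Grade 2 event.

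- **Protocol 4.5.3, Table 4.5.3-1.** The text says the table "describes the recommended dose modifications for brentuximab vedotin treatment associated toxicity". At Grade 2, the hematologic row and the row for non-hematologic toxicity other than neuropathy both read "Continue at same dose level". The neuropathy row reads "Reduce dose to 1.2 mg/kg and resume treatment". Withholding first appears in the Grade 3 cells.
- **Protocol 4.5.4.1.** It opens with "Dose delay criteria apply for all drug-related AEs" and lists as a trigger "Any Grade ≥ 2 non-skin, drug-related AE, with the following exceptions". The exemption is "Grade 2 drug-related fatigue or laboratory abnormalities do not require a treatment delay". A more specific line covers AST, ALT and total bilirubin: if the baseline is normal, "delay dosing for drug-related Grade ≥ 2 toxicity".
- **Protocol 4.5.4.2.** Nivolumab restarts at Grade 1 or lower, or baseline, with listed exceptions (diarrhea must return to baseline). Then: "If nivolumab treatment is delayed for any reason, brentuximab vedotin must also be delayed until the subject has appropriately recovered". Section 4.5.3 has the mirror rule, and SAP 7.4.2.1 repeats the link. A delay of more than 6 weeks ends study therapy, except as Section 4.5.5 allows.

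Under Protocol 4.5.1, a DLT is a study-drug-related toxicity that requires a reduction of either drug, or a delay of either by more than 7 days, in Cycle 2, or that delays combined dosing at Cycle 3 Day 1 by more than 7 days. SAP 7.6.1 tabulates DLTs on that basis. Two or more DLTs in six subjects rule out expansion as the next step.

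**The concern.** A site facing, say, Grade 2 drug-related diarrhea finds one section telling it to go on with brentuximab vedotin and another telling it to hold nivolumab, and therefore brentuximab vedotin too. It cannot do both, and no sentence ranks them. Sites that resolve this differently deliver different treatment for the same event.

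Adverse events leading to dose delay and to discontinuation are primary safety endpoints (Protocol 8.3.1, SAP 4.1), so the counts would partly reflect which section each site followed. The DLT definition is also built on reductions and delays, so the same ambiguity can reach the Cohort A count.

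**Working it through.** **Step 1. The rules side by side, for a Grade 2 drug-related event**

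| Event | Table 4.5.3-1 | 4.5.4.1 with 4.5.4.2, read literally | Compatible? |
|---|---|---|---|
| Non-skin, non-laboratory, not fatigue (e.g. diarrhea) | Continue, same dose | Both drugs held to Grade 1 or baseline (diarrhea: baseline) | No |
| Peripheral neuropathy | Reduce and resume | Both drugs held to Grade 1 or baseline | No |
| AST, ALT or bilirubin, normal baseline | Continue, same dose | Both drugs held to Grade 1 or baseline | No |
| Skin, fatigue, other laboratory values (most of the hematologic row) | Continue, same dose | No mandatory hold at Grade 2 | Yes |

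The third row takes the specific liver-test line as overriding the general laboratory exemption.

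**Step 2. Persistent neuropathy.** Protocol 3.3.2 excludes neuropathy of Grade 2 or higher at entry, so a subject still at Grade 2 cannot restart through the return-to-baseline route. Under the literal hold, both drugs stay off until Grade 1. After more than 6 weeks 4.5.4.2 requires permanent discontinuation, unless a 4.5.5 exception applies. Under the table, treatment goes on at the reduced dose.

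**Step 3. What *drug-related* covers.** Protocol 6 defines relatedness to study drug, 4.1 names both agents as investigational products, and 4.5.3 names brentuximab vedotin where it means that agent alone. Against that, 4.5.4.1 sits under a nivolumab heading, and 4.5.1 names both agents where it means either. If the term means nivolumab-related only, the conflict disappears for events attributed purely to brentuximab vedotin. It remains for events attributed to both agents.

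**Step 4. DLT class**

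- *Diarrhea, liver tests and the like.* If the nivolumab hold applies and exceeds 7 days in the window, that alone is a DLT, because the definition counts either drug. The linked brentuximab vedotin delay adds nothing. The class differs only if another reading (table governs the regimen, or *drug-related* means nivolumab-related) gives no hold at all.
- *Neuropathy.* The table's required reduction in Cycle 2 is already a DLT, and so is a hold of more than 7 days. The event escapes only if the hold comes first, it falls to Grade 1 within 7 days, and dosing resumes unreduced under the Grade 1 cell.

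**Step 5. The figure that the DLT count feeds.** Protocol 8.1 gives one-sided 80% exact upper limits. The limit for x of n is the 0.80 quantile of Beta(x+1, n−x).

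- 1/6: Beta(2, 5) gives 42.24% (plan: 42%).
- 3/12: Beta(4, 9) gives 41.24% (plan: 41.2%).
- 2/6: Beta(3, 4) gives 58.54%.

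One subject reclassified from 1/6 to 2/6 moves the limit by 58.5 − 42.2 = 16.3 percentage points and crosses the expansion threshold.

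**Step 6. Illustration with assumed rates (none are in the documents).** Let p be the undisputed DLT rate and q the share of the remaining subjects with a disputed hold of more than 7 days. The total rate is t = p + (1−p)q, and P(at most 1 of 6) = (1−t)^6 + 6t(1−t)^5. For p = 0.20 and q = 0.10, t = 0.28 and the probability is 0.464, against 0.655 at q = 0.

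| p | q = 0 | 0.05 | 0.10 | 0.20 | 0.30 |
|---|---|---|---|---|---|
| 0.10 | 0.886 | 0.788 | 0.680 | 0.464 | 0.283 |
| 0.20 | 0.655 | 0.558 | 0.464 | 0.301 | 0.176 |
| 0.30 | 0.420 | 0.348 | 0.283 | 0.176 | 0.100 |

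This shows how sensitive a threshold of two in six is. It does not estimate how often a dispute occurs.

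**The case against.** The best defence is an overlay reading. The table is only recommended and covers brentuximab vedotin toxicity. The linked rule stands in the same section, is mandatory, applies whatever the reason, and is repeated in 4.5.4.2 and the SAP. A site would check each drug's own criteria and hold both if either requires it; reduce and resume can then follow the hold. The narrower meaning of *drug-related* would also remove the conflict for events attributed to brentuximab vedotin alone.

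The overlay is workable, but the protocol does not state it. It also leaves table cells without effect. Grade 2 neuropathy could not resume at a reduced dose while still Grade 2, and the Grade 3 cells that allow a restart at Grade 2 would be overridden wherever 4.5.4.2 requires Grade 1. The narrower meaning is possible, but the opening line of 4.5.4.1 points the other way.

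Two further points stand and limit the consequence. In 4.5.1 the study team may overturn a DLT classification. SAP 7.1 says only one dose was explored in Cohort A and pools that cohort with Cohort B, which suggests that the dose decision had been made by the SAP date of January 2017. The delay and discontinuation counts are also descriptive; no test depends on them.

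**Conclusion.** The contradiction is real for the three incompatible rows in Step 1, and it goes beyond missing detail: for persistent Grade 2 neuropathy the readings diverge between continuing and ending therapy. It affects treatment delivered and two primary safety counts, and applies to the 130 subjects planned for Cohort B. This rests on the literal wording of 4.5.4.1 and 4.5.4.2 and on the absence of any statement of precedence.

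Three stronger readings are tempting, and the documents do not support them.

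- *Every Grade 2 drug-related event is in conflict.* Skin events, fatigue and most laboratory abnormalities do not trigger the nivolumab hold.
- *The linked delay itself flips DLT class.* It does not, because the definition already counts either drug. A change needs a hold of more than 7 days in the window on one reading and none on the other, or the short neuropathy path in Step 4.
- *The 45% neuropathy figure in Protocol 1.4.4 shows that the conflict is frequent.* It is any-grade sensory neuropathy over whole single-agent studies, with no Grade 2 share and no timing relative to a 6-week window. The documents give no frequency.

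Any effect on the Cohort A decision is probably past. What remains there is how SAP 7.6.1 tabulates DLTs.

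**What to change.** Reconcile Protocol Table 4.5.3-1, 4.5.4.1 and 4.5.4.2, and SAP 7.4.2.1 with them:

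1. Define *drug-related* in 4.5.4.1: related to nivolumab, or to either agent.
2. State which provision governs a Grade 2 event attributed to one agent, including Grade 2 neuropathy that does not resolve.
3. Apply the same rule in the DLT definition (Protocol 4.5.1) and tabulation (SAP 7.6.1), and say whether a delay imposed only by the link counts.

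Which clinical rule should prevail is for the sponsor and the investigators; this point takes no position on it. The cost is wording in the next protocol amendment and a matching SAP update, with no change to sample size or analysis method. If Cohort A is complete, re-reading its DLT listing under the stated rule would show whether any classification depended on the ambiguity.
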